AE	Adverse Event
ATC	Anatomical Therapeutic Chemical
BCVA	Best Corrected Visual Acuity
BDCVA	Best Distance-Corrected Visual Acuity
BID	Twice Daily
CI	Confidence Interval
eCRF	Electronic Case Report Form
ETDRS	Early Treatment of Diabetic Retinopathy Study
FAS	Full Analysis Set
GEE	Generalized Estimating Equation
ICF	Informed Consent Form
ICH	International Council for Harmonisation
IMDF	Imputing Missing Data as Failures
IOP	Intraocular Pressure
IP	Investigational Product
IRT	Interactive Response Technology
HIPAA	Health Information Portability and Accountability Act
LDPE	Low-Density Polyethylene
LL-BDCVA	Low-Luminance Best Distance-Corrected Visual Acuity
logMAR	Logarithm of the Minimum Angle of Resolution
LS	Least Square
MCMC	Markov Chain Monte Carlo
MedDRA	Medical Dictionary for Regulatory Activities
MI	Multiple Imputation
NCS	Not Clinically Significant
ODO	Observed Data Only
PPS	Per Protocol Set
PT	Preferred Term
SAE	Serious Adverse Event
SAF	Safety Set
SAP	Statistical Analysis Plan
SD	Standard Deviation
SDC	Statistics & Data Corporation
SOC	System Organ Class
TEAE	Treatment-Emergent Adverse Event
TPA	Tipping Point Analysis
VA	Visual Acuity
WHO	World Health Organization

1. Introduction

The purpose of this statistical analysis plan (SAP) is to describe the planned analyses and reporting for the Orasis 20-150-0003 protocol, Version 2.0 (Amendment 1), dated 07Jan2021 (NEAR-2 study).

This Version 2.0 SAP replaces the previous finalized and signed Version 1.0 SAP, dated 22Nov2021.

This SAP is being written with due consideration of the recommendations outlined in the most recent International Council for Harmonisation (ICH) E9 Guideline entitled Guidance for Industry: Statistical Principles for Clinical Trials and the most recent ICH E3 Guideline entitled Guidance for Industry: Structure and Content of Clinical Study Reports.

This SAP describes the data that will be analyzed and the subject characteristics, efficacy, and safety assessments that will be evaluated. This SAP provides details of the specific statistical methods that will be used. The statistical analysis methods presented in this document will supersede the statistical analysis methods described in the clinical protocol. Any additional analyses required to supplement the planned analyses described in this SAP will be duly noted in the clinical study report.

2. Study Objectives

The primary objective of this study is to evaluate the efficacy of CSF-1 (0.4% pilocarpine hydrochloride ophthalmic solution) for the temporary correction of presbyopia.

The secondary objectives of this study are to evaluate the safety and tolerability of CSF-1 versus Vehicle.

2.1 Study Variables

For all study variables, baseline is defined as the pre-treatment measurement taken at Visit 2 (Day 1). If the measurement is not available from Visit 2 (Day 1), then the measurement from Visit 1 (Day -14 to -1) will be used as baseline for all treatments/visits. Change from baseline will be calculated as follow-up measure minus baseline measure.

Efficacy variables include best distance-corrected visual acuity (BDCVA) at 40 cm (Precision Vision Chart) and BDCVA at 4 m (Early Treatment of Diabetic Retinopathy Study [ETDRS] chart), [REDACTED]

[REDACTED].

Safety variables include BDCVA at distance under normal and low-luminance testing conditions, slit-lamp biomicroscopy measures, conjunctival redness grading, and study drug drop comfort assessment, as well as intraocular pressure (IOP), dilated indirect fundoscopy, and adverse events (AEs). The logarithm of the minimum angle of resolution (logMAR) units will be used for all VA safety and efficacy measures. Visual acuity will be assessed with best distance-correction determined by the manifest refraction at Visit 1 (Day -14 to -1). Further details regarding the procedures for conducting manifest refraction can be found in the BCVA protocol.

2.2 Primary Efficacy Endpoint

Percentage of subjects with a \geq 3-line (15-letter) gain, from baseline, in BDCVA at 40 cm (Precision Vision chart) and no loss in BDCVA \geq 5 letters (ETDRS chart at 4 m) in the study eye at Visit 3 (Day 8), following Dose 1, 1 hour post-treatment.

2.3 Secondary Efficacy Endpoints

2.3.1 KEY SECONDARY EFFICACY ENDPOINTS

Key secondary efficacy endpoints include the following:

Percentage of subjects with a \geq 3-line (15-letter) gain, from baseline, in BDCVA at 40 cm (Precision Vision chart) and no loss in BDCVA \geq 5 letters (ETDRS chart at 4 m) in the study eye at the following Visits, Doses and timepoints:

Visit 3 (Day 8)

Dose 1

- 2 hours following Dose 1

Dose 2

- 1 hour following Dose 2
- 2 hours following Dose 2

[REDACTED]

[REDACTED]

[REDACTED]

[REDACTED]

[REDACTED]

[REDACTED]

2.5 Safety Endpoints

The safety endpoints include the following:

- BDCVA (normal and low luminance) at 4 m
- Slit-lamp biomicroscopy
- Conjunctival redness grading
- Study drug drop comfort assessment
- IOP
- Dilated indirect fundoscopy
- AEs (reported, elicited, and observed)

2.6 Statistical Hypotheses

The primary efficacy hypothesis is:

H_{01} : The difference between study eyes treated with CSF-1 and study eyes treated with Vehicle, in the percentage of study eyes with a ≥ 3 -line (15-letter) improvement from baseline in BDCVA at 40 cm (Precision Vision chart) without a loss in BDCVA of ≥ 5 letters (ETDRS at 4 m) at Visit 3 (Day 8), 1 hour post-dose 1 = 0

H_{11} : The difference between study eyes treated with CSF-1 and study eyes treated with Vehicle, in the percentage of study eyes with a ≥ 3 -line (15-letter) improvement from baseline in BDCVA at 40 cm (Precision Vision chart) without a loss in BDCVA of ≥ 5 letters (ETDRS at 4 m) at Visit 3 (Day 8), 1 hour post-dose 1 \neq 0

The study will be considered a success if the null hypothesis, H_{01} , is rejected at a 2-sided alpha = 0.05 in favor of CSF-1 in the alternative hypothesis, H_{11} , tested as delineated in the primary efficacy analysis section, and the following secondary efficacy hypotheses will each be tested as stated under adjustments for multiplicity.

The key secondary efficacy hypotheses are:

Visit 3 (Day 8)

Visit 3, 2 Hours Post-Dose 1

H_{02} : The difference between study eyes treated with CSF-1 and study eyes treated with Vehicle, in the percentage of study eyes with a ≥ 3 -line (15-letter) improvement from baseline in BDCVA at 40 cm (Precision Vision chart) without a loss in BDCVA of ≥ 5 letters (ETDRS at 4 m) at Visit 3 (Day 8), 2 hours post-dose 1 = 0.

H_{12} : The difference between study eyes treated with CSF-1 and study eyes treated with Vehicle, in the percentage of study eyes with a ≥ 3 -line (15-letter) improvement from baseline in BDCVA at 40 cm (Precision Vision chart) without a loss in BDCVA of ≥ 5 letters (ETDRS at 4 m) at Visit 3 (Day 8), 2 hours post-dose 1 \neq 0.

Visit 3, 1 Hour Post-Dose 2

H_{03} : The difference between study eyes treated with CSF-1 and study eyes treated with Vehicle, in the percentage of study eyes with a ≥ 3 -line (15-letter) improvement from baseline in BDCVA at 40 cm (Precision Vision chart) without a loss in BDCVA of ≥ 5 letters (ETDRS at 4 m) at Visit 3 (Day 8), 1 hour post-dose 2 = 0.

H_{13} : The difference between study eyes treated with CSF-1 and study eyes treated with Vehicle, in the percentage of study eyes with a ≥ 3 -line (15-letter) improvement from baseline in BDCVA at 40 cm (Precision Vision chart) without a loss in BDCVA of ≥ 5 letters (ETDRS at 4 m) at Visit 3 (Day 8), 1 hour post-dose 2 \neq 0.

Visit 3, 2 Hours Post-Dose 2

H_{04} : The difference between study eyes treated with CSF-1 and study eyes treated with Vehicle, in the percentage of study eyes with a ≥ 3 -line (15-letter) improvement from baseline in BDCVA at 40 cm (Precision Vision chart) without a loss in BDCVA of ≥ 5 letters (ETDRS at 4 m) at Visit 3 (Day 8), 2 hours post-dose 2 = 0.

H_{14} : The difference between study eyes treated with CSF-1 and study eyes treated with Vehicle, in the percentage of study eyes with a ≥ 3 -line (15-letter) improvement from baseline in BDCVA at 40 cm (Precision Vision chart) without a loss in BDCVA of ≥ 5 letters (ETDRS at 4 m) at Visit 3 (Day 8), 2 hours post-dose 2 \neq 0.

[REDACTED]

[REDACTED]

[figure not shown]
[REDACTED]

[figure not shown]
[REDACTED]

[figure not shown]
[REDACTED]

[REDACTED]

[REDACTED]

3. Study Design and Procedures

3.1 Overall Study Design

This is a four-visit multi-center, randomized, double-masked, parallel-group study evaluating the safety and efficacy of CSF-1 compared with Vehicle in approximately 300 subjects with presbyopia. The study design is summarized in [Figure 1](#).

Visit 1 (Screening, Day -14 to -1): Qualified subjects will receive 1 drop of Vehicle instilled in each eye, followed by preliminary efficacy assessments to identify Vehicle responders at 15 minutes post-vehicle instillation.

Vehicle responder is defined as a subject who had a > 0.14 LogMAR (i.e., 7 letters) improvement in post-Vehicle treatment (at 15 minutes post-Vehicle treatment) monocular BDCVA in either eye at 40 cm compared to Visit 1 pre-treatment, or a > 0.14 LogMAR (i.e., 7 letters) improvement in monocular BDCVA in either eye at 40 cm between Visit 1 (pre-treatment) and Visit 2 (pre-treatment baseline).

Visit 2 (Day 1): Baseline assessments. Subjects who meet all inclusion and none of the exclusion criteria and qualify as Vehicle non-responders, will be randomized 1:1 to one of the following treatment arms:

- CSF-1 (0.4% pilocarpine hydrochloride ophthalmic solution)
- Vehicle

Pre-treatment measurements taken at this visit are considered as baseline.

[figure not shown]
At the Visit 2 (Day 1) clinic visit, study personnel will instill Dose 1 of study drug at 8:30 AM \pm 30 minutes in each eye. Efficacy and safety assessments will be conducted for 2 hours following Dose 1. Dose 2 will be instilled by study personnel at 10:30 AM \pm 30 minutes in each eye. Efficacy and safety assessments will be conducted for 4 hours following Dose 2.

All subjects will be instructed to dose twice daily (BID) with a single drop in each eye for approximately 1 week. The first daily dose should occur in the morning, with the second dose following 2 hours later (± 1 hour). Subjects will be instructed not to dose at home on clinic visit days.

Visit 3 (Day 8): Study personnel will instill Dose 1 of study drug at 8:30 AM \pm 30 minutes in each eye. Efficacy and safety assessments will be conducted for 2 hours following Dose 1. Dose 2 will be instilled by study personnel at 10:30 AM \pm 30 minutes in each eye. Efficacy and safety assessments will be conducted for 2 hours following Dose 2.

All subjects will be instructed to dose twice daily (BID) with a single drop in each eye, for approximately 1 week. The first daily dose should occur in the morning with the second dose following 3 hours later (± 1 hour). Subjects will be instructed not to dose at home on clinic visit days.

Visit 4 (Day 15): Study personnel will instill Dose 1 of study drug at 8:30 AM \pm 30 minutes in each eye. Efficacy and safety assessments will be conducted up to 3 hours following Dose 1. Dose 2 will be instilled by study personnel at 11:30 AM \pm 30 minutes in each eye. Efficacy and safety assessments will be conducted for 5 hours following Dose 2.

[figure not shown]
Figure 1. Study Design

[figure not shown]
3.2 Schedule of Visits and Measurements

The schedule of visits and assessments is provided in [Table 1](#).

Table 1 Schedule of Visits and Assessments

Visit Number	Visit Type	Assessment	Frequency	Comments
1	Initial Visit	Demographic Data	Once	
2	Mid-Treatment Visit	Physical Examination	Every 6 months	
3	Final Visit	Overall Health Status	Once	
4	Follow-up Visit	Health Monitoring	As needed	

4. Study Treatments

The investigational product (IP) is CSF-1, a sterile topical eye drop solution. The formulation developed by Orasis Pharmaceuticals Ltd. is a preservative-free eye drop, containing the active ingredient pilocarpine hydrochloride 0.4%, with the addition of standard pharmacopoeial excipients used in sterile ophthalmic solutions.

The vehicle (CSF-1 placebo) is a topical eye drop solution containing the same ingredients as in CSF-1 except for the active ingredient.

Both IP and Vehicle are packaged in a single-dose transparent low-density polyethylene (LDPE) vials, enclosed within a pouch. Each pouch includes five vials. Kits will be dispensed to subjects at Visit 2 (Day 1) and Visit 3 (Day 8) with 1 week of at-home dosing in each kit. CSF-1 will be evaluated for comparison to Vehicle.

Following the pre-treatment assessments, qualified subjects will be randomized to 1:1 to one of the following treatment arms:

1. CSF-1: Pilocarpine Hydrochloride (0.4%) Ophthalmic Solution
2. Placebo (Vehicle)

After randomization at Visit 2 (Day 1), subjects will receive study drug and a paper dosing diary. Each subject will instill one drop of study drug to each eye and keep aside the used vial to be returned to the site

at next visit for compliance check. Following Visit 2, subjects will be instructed to dose bilaterally BID (with 2 hours (+1 hour) between doses) and record doses in their diary until Visit 3. Subjects should not dose at home on day of Visit 3. Following Visit 3, after subjects receive their study drug and dosing diary, subjects will be instructed to dose bilaterally BID (with 3 hours (+1 hour) between doses) and record doses in their diary until Visit 4. Subjects should not dose at home on day of Visit 4. At Visit 4, subjects will receive their doses at the visit by study personnel after the required pre-treatment assessments and their study drug will be collected. Subjects will exit the study after all assessments are complete at Visit 4.

4.1 Method of Assigning Subjects to Treatment Groups

Each subject who signs an informed consent form (ICF) will be assigned a subject number. Subject numbers will be assigned in sequential order beginning with 001. Once a subject meets all qualification criteria at Visit 2 (Day 1), they will be randomized in a 1:1 ratio via an Interactive Response Technology (IRT) system to one of the following treatment groups: (1) CSF-1 or (2) Vehicle, and stratified by iris color (brown versus light [i.e., blue, green, gray, and hazel]) and by baseline manifest refraction spherical equivalent <-0.5 D, -0.5 D to +0.75 D, and >+0.75 D); randomization will not be stratified by site.

At least, approximately, 30% of subjects will have a light iris and at least, approximately, 30% will have a brown iris. The actual percentages will vary based on enrollment.

Randomization will be used to avoid bias in the assignment of subjects to treatment, to increase the likelihood that known and unknown subject attributes (e.g., iris color and baseline characteristics) are evenly balanced across treatment groups, and to enhance the validity of statistical comparisons across treatment groups. Double-masked treatment will be used to reduce the potential of bias during data collection and the evaluation of clinical endpoints.

4.2 Masking and Unmasking

An independent, unmasked biostatistician who is not otherwise involved in the trial will generate the complete randomized study drug kit list. The subject, study sponsor, medical investigators, and study staff will be masked during the entire randomization process and throughout the course of the study. When medically necessary, the investigator may need to determine what treatment has been assigned to a particular subject. When possible (i.e., in non-emergent situations), [REDACTED] and/or the study sponsor should be notified before unmasking the IP. In emergency situations, the investigator must notify the sponsor within 24 hours after determining that it is necessary to unmask the treatment assignment. The investigator must also indicate in source documents and in the electronic case report form (eCRF) that the mask was broken and provide the date, time, and reason for breaking the mask.

5. Sample Size and Power Considerations

A total sample size of 280 subjects (140 subjects per arm) yields > 97.5% power to establish superiority of CSF-1 to Vehicle in the percentage of study eyes demonstrating a \geq 3-line (15-letter) gain from baseline in BDCVA at 40 cm (Precision Vision chart) and no loss of BDCVA \geq 5 letters (ETDRS at 4 m), 1-hour post

each dose on Visit 3 (Day 8) assuming a response rate of 42.5% in CSF-1 and 17.5% in Vehicle using a Pearson chi-squared test with a 2-sided significance level of 0.05.

A series of horizontal black bars of varying lengths, likely representing redacted text or data. The bars are arranged vertically and span the width of the page. Some bars are longer, while others are shorter, indicating different lengths of redacted content.

Accounting for approximately a 5% discontinuation rate, approximately 150 subjects per arm (approximately 300 total) will be randomized.

6. Data Preparation

All reported study data will be recorded on the eCRFs supplied by [REDACTED] using iMedNet™. Only the Principal Investigator and authorized study staff according to the Delegation of Responsibilities log are entitled to make entries in the eCRF. After data are entered into the clinical study database, electronic edit checks, and data review will be performed. All data validation specifications and procedures are detailed in the Data Validation Manual as a separate document. When the database has been declared to be complete and accurate, the database will be locked. Any changes to the database after data have been locked can only be made with the approval of the sponsor and [REDACTED] Inc. in consultation with SDC.

The final analyses outlined in this document will be carried out only after the following have occurred:

- All data management requirements are met according to SDC standard operating procedures, including data entry, performance of edit and validation checks, documentation and resolution of data queries, and database lock with written authorization provided by appropriate SDC and sponsor personnel.

- Protocol deviations have been identified and status defined (major/minor deviations), and completed prior to database lock and study unmasking.
- Analysis populations have been determined, and completed prior to database lock and study unmasking.
- Randomized treatment codes have been unmasked.

7. Analysis Sets

7.1 Full Analysis Set

The full analysis set (FAS) will include all randomized subjects who have received at least one dose of the study drug. Subjects in the FAS will be analyzed as randomized. The FAS analysis set will be the primary analysis set for the determination of efficacy.

7.2 Per Protocol Set

The per-protocol set (PPS) will include subjects in the FAS who do not have significant protocol deviations that affect the primary efficacy endpoint analyses. Protocol deviations will be assessed prior to database lock and unmasking. Subjects in the PPS will be analyzed as treated. The PPS analysis will be supportive of the primary and key secondary efficacy analysis performed with FAS.

7.3 Safety Set

The safety set (SAF) will include all subjects who have received at least one dose of the study drug. Subjects in the SAF will be analyzed as treated.

8. General Statistical Considerations

8.1 Unit of Analysis

The study eye will be used for all monocular analyses. The fellow eye will inherently be included in all binocular analyses. Both eyes will be displayed and analyzed for all ophthalmic safety endpoints.

The study eye will be defined by the study Investigator as the eye that meets all enrollment criteria. If both eyes meet all enrollment criteria, then the eye with the worse Visit 2 pre-treatment/baseline BDCVA at 40 cm (Precision Vision chart) will be the study eye. If both eyes have the same BDCVA at 40 cm, the right eye will be the study eye.

8.2 Missing Data Handling and Sensitivity Analysis

The primary efficacy analysis and the key secondary analyses will be performed on the FAS, as described in [section 12.1](#). In the event of missing data, the primary imputation method will be Multiple Imputation (MI), using randomized treatment-based Markov Chain Monte Carlo (MCMC). Sensitivity analyses will also be performed on the primary and key secondary efficacy endpoints measured at Visit 3 (Day 8). These sensitivity analyses will be considered supportive of the primary and key secondary analyses.

8.3 Definition of Baseline

For all endpoints, baseline is defined as the pre-randomization measurement taken at Visit 2 (Day 1). If the measurement is not available from Visit 2 (Day 1), then the measurement from Visit 1 (Day -14 to -1) will be used as baseline. Change from baseline will be calculated as: Post-Baseline Measure – Baseline Measure.

8.4 Data Analysis Conventions

All data analysis will be performed by SDC after the study is completed and the database has been locked and released for unmasking. Statistical programming and analyses will be performed using SAS® Version 9.4 or higher. Output will be provided in rich text format for tables and portable document format for tables, listings, and figures using landscape orientation. All study data will be listed by subject, treatment, and visit (as applicable) based on all randomized subjects unless otherwise specified.

Summaries for continuous and ordinal variables will include the number of observations, arithmetic mean, standard deviation (SD), median, minimum, and maximum. Minima and maxima will be reported with the same precision as the raw values; means and medians will be presented to 1 additional decimal place than reported in the raw values. Standard deviations will be presented to 2 additional decimal places than reported in the raw values. Summaries for discrete variables will include frequency counts and percentages. All percentages will be rounded to 1 decimal place (i.e., XX.X%). Change from baseline will be calculated as baseline subtracted from the relevant post-baseline visit (Post-Baseline Visit – Baseline Visit), with baseline defined in [Section 8.3](#) of this SAP.

Gains or improvements in BDCVA at 40 cm (Precision Vision chart) of \geq 3-lines (15-letters) are defined as changes from baseline in BDCVA at 40 cm (Precision Vision chart) of \leq -0.30 logMAR (e.g., -0.30, -0.32, ... logMAR).

Gains or improvements in BDCVA at 40 cm (Precision Vision chart) of \geq 2-line (10-letters) are defined as changes from baseline in BDCVA at 40 cm (Precision Vision chart) of \leq -0.20 logMAR (e.g., -0.20, -0.22, ... logMAR).

[figure not shown]
Similarly, loss in BDCVA of \geq 5 letters (ETDRS at 4 m) are defined as changes from baseline in BDCVA (ETDRS at 4 m) of \geq 0.10 logMAR (e.g., 0.10, 0.12, ... logMAR).

All statistical tests, unless otherwise indicated, will be 2-sided with a significance level of 0.05 ($\alpha = 0.05$). Confidence intervals (CI) for differences between treatment groups will be 2-sided at 95% confidence. All p-values will be rounded to 4 decimal places; p-values less than 0.0001 will be presented as " <0.0001 "; p-values greater than 0.9999 will be presented as " >0.9999 ." Unless otherwise specified, summaries will be presented by treatment group and, where appropriate, visit.

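### Does comparing logMAR changes with -0.30 and 0.10, with no stated rounding rule, misclassify subjects who sit exactly on the responder threshold?

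*SAP*

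**What the plan says.** The endpoint is set in letters: a gain of at least 15 at 40 cm with no loss of 5 or more at 4 m, at Visit 3, 1 hour after Dose 1 (SAP 2.2; protocol 6.1). The SAP then works in logMAR.

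- SAP 2.1: "The logarithm of the minimum angle of resolution (logMAR) units will be used for all VA safety and efficacy measures".
- SAP 8.4, change score: "Change from baseline will be calculated as baseline subtracted from the relevant post-baseline visit (Post-Baseline Visit – Baseline Visit").
- SAP 8.4, gain: 3-line gains "are defined as changes from baseline in BDCVA at 40 cm (Precision Vision chart) of" at or below minus "0.30 logMAR (e.g., -0.30, -0.32, ... logMAR"). The value -0.30 is the first example of a gain.
- SAP 8.4, loss: at or above "0.10 logMAR (e.g., 0.10, 0.12, ... logMAR"). The value 0.10 is the first example of a loss.
- SAP 8.4, software: "Statistical programming and analyses will be performed using SAS® Version 9.4 or higher".
- SAP 3.1 gives the scale, "0.14 LogMAR (i.e., 7 letters) improvement in post-Vehicle treatment", which is 0.02 logMAR per letter.

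SAP 8.4 has display rules for means, SDs, percentages and p-values, but no rounding or tolerance for the change score. SAP 12.1 imputes the continuous acuities and derives response afterwards. Its logistic model code starts from a finished yes/no indicator, so the derivation itself is not shown. The notes to that code describe the baseline covariate in letters.

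**The concern.** Two-decimal logMAR values such as 0.58 have no exact binary representation. Subtracting two of them can leave an error in the last digit, and the SAP's cut-offs lie on the measurement grid, so exact ties are possible. If a programmer compared the raw difference with -0.30 or 0.10, two subjects with the same 15-letter gain could receive different outcomes only because their baselines differ. An exact 5-letter loss could pass as no loss and leave the subject a responder against the endpoint's distance-vision condition.

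The same derivation feeds the primary endpoint, the three hierarchical key secondary endpoints (SAP 8.5) and the sensitivity analyses (SAP 12.2). The SAP's methods also supersede the protocol's (SAP Introduction). At stake would be a small number of wrong subject-level outcomes and a responder count that two programmers might not reproduce identically.

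**Working it through.** **Inputs.** Cut-offs -0.30 and 0.10, both inclusive (SAP 8.4). Step of 0.02 logMAR per letter, from 0.14 = 7 letters (SAP 3.1). Range -0.30 to 1.00, the imputation bounds in SAP 12.1. Response rates 42.5% and 17.5%, 140 per arm, two-sided 0.05, stated power above 97.5% (SAP 5).

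**1. Are the cut-offs right?** 15 × 0.02 = 0.30 and 5 × 0.02 = 0.10. Both match the letter endpoint.

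**2. The plan's own power figure.** With p1 = 0.425, p2 = 0.175 and mean rate 0.30:

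- SE under the null = √(2 × 0.30 × 0.70 / 140) = 0.05477
- SE under the alternative = √((0.425 × 0.575 + 0.175 × 0.825) / 140) = 0.05270
- z = (0.25 - 1.96 × 0.05477) / 0.05270 = 2.707, so power = 99.66%

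The stated lower bound is met.

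**3. What a raw comparison would do.** This was checked in IEEE double precision in Python. SAS was not run; the check assumes that it stores 8-byte IEEE numbers and compares them without a tolerance.

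| Baseline → post | Letters | Computed change | Naive result |
|---|---|---|---|
| 0.56 → 0.26 | 15 gained | -0.30000000000000004 | gain |
| 0.58 → 0.28 | 15 gained | -0.29999999999999993 | gain missed |
| 0.00 → 0.10 | 5 lost | 0.1 | loss |
| 0.02 → 0.12 | 5 lost | 0.09999999999999999 | loss missed |

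- Exact 15-letter gains, baselines 0.40 to 1.00: 8 of 31 missed (0.58, 0.70, 0.82, 0.84, 0.86, 0.94, 0.96, 0.98). Only one of the 15 grid values from 0.40 to 0.68 is among them.
- Exact 5-letter losses, baselines -0.30 to 0.20: 8 of 26 missed.
- No 14-letter gain or 4-letter loss is wrongly counted.
- The set depends on how logMAR is stored. Over the 51 exact 15-letter gains that fit in -0.30 to 1.00, 8 fail with two-decimal values, 6 if logMAR is letters × 0.02, and 18 if it is 1.1 - 0.02 × letters.

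**4. What the written rule does.** A change of -0.30 is a gain and 0.10 is a loss, by the SAP's own examples. Every exact tie is therefore classified as the letter endpoint requires. With differences rounded to two decimals, or compared with a tolerance of 1e-8, none of the 51 gains and none of the 61 losses on the grid is misread.

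**5. Size if the slip did occur.** The acuity entry criteria are redacted and no distribution at the threshold is given, so any figure needs assumptions. With mean baseline 0.55 to 0.70 and a gain SD of 6.5 letters (both assumed), the CSF-1 rate falls by 0.3 to 1.0 points and the Vehicle rate by 0.3 to 0.7. Missed gains and missed losses act in opposite directions. Using the formula in step 2:

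| CSF-1 | Vehicle | Power |
|---|---|---|
| 42.5% | 17.5% | 99.66% |
| 41.5% | 16.8% | 99.64% |
| 41.5% | 17.5% | 99.43% |

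A deliberately harsh case puts 10% of CSF-1 subjects exactly at 15 letters and misreads half of them: 42.5 - 5.0 = 37.5%. With Vehicle unchanged, power is 96.7%. If Vehicle loses 2.0 points as well (15.5%), it is 98.9%.

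**6. Rounding to 0.01 as a rule.** Imputed acuities are continuous and off the 0.02 grid. An imputed change of -0.296 would round to -0.30 and become a response, although SAP 8.4 does not count it as one. An imputed 0.096 would become a loss.

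**The case for a change.** The strongest case for acting is that the affected variable is the primary endpoint and that the SAP takes care over display rounding yet says nothing about the one derived number that decides response. Ties are to be expected on a discrete scale. Two competent programmers who build logMAR differently could obtain different counts. One sentence before unmasking would settle it, and letter scores may already be in the data.

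Most of the facts in this stand: the arithmetic is correct, no tolerance is stated, and an explicit rule would cost almost nothing. What does not stand is the step from an unstated safeguard to a wrong rule. The SAP names both boundary values as included, so a programmer has a definite answer to check the code against, and code that rejects an exact 15-letter gain fails that check. The two programmers would differ only if at least one of them failed to carry out the written definition. An obvious one-sentence addition, rounding to 0.01 for all values, would also introduce an error for imputed data that the present wording does not have.

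**Conclusion.** No change to the plan is needed. The cut-offs are correct, the boundary values are explicitly included, and following the SAP as written gives the right outcome for every exact 15-letter gain and every exact 5-letter loss. What is missing is a detail of numerical handling that a statistical programmer ordinarily supplies, by classifying observed data on whole letters or by using a very small tolerance.

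The number of subjects who could be affected cannot be derived from the documents. Under the assumed distributions in the working, rates would move by at most 1.0 point and power would stay between about 99.4% and 99.7%. Only the harsh one-arm case, with half of a 10% share of ties lost in CSF-1 and none in Vehicle, takes power slightly below the stated bound, to 96.7%. A missed gain can only remove responders. A missed loss can add one, which partly offsets this. For given acuity values neither error depends on the treatment arm.

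The conclusion rests on two readings of the documents: that the listed examples in SAP 8.4 define the boundary, and that the unseen derivation code follows them.
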